 - In vitro response: ELISPOT assays, measuring IFN- γ production in the peripheral blood of treated patients. Compare specific immune responses after each therapy cycle by measuring IFN- γ production by tumor-specific CTLs. Radioactive chromium releases cytotoxic assays to measure CTL and NK-mediated antitumor response. After each therapy cycle, ELISA assays for quantifying cytokines (IFN- γ , IL-10) in patient serum.
- **CLINICAL RESPONSE MEASUREMENT:** To observe the objective response rate. The percentage of patients with complete response (CR) and patients with partial response (PR) will be reported.

SECONDARY SPECIFIC AIMS:

To evaluate:

- Overall Survival.
- Disease-Free Survival.
- Quality of Life (assessed using EORTC global QLQ-C30 and EORTC disease-specific QLQ).
- Performance status response: The percentage of patients with a 20% or more significant increase in activity measured by the Karnofsky index will be reported.

MATERIAL AND METHODS

Dendritic Cell Generation: Patient leukocytes will be obtained through leukapheresis at the Blood Bank of the Clinical Hospital of the UNIVERSITY OF CHILE, following the standard protocols used in that unit. Peripheral blood mononuclear cells (PBMCs) will be isolated from peripheral blood using a Ficoll-Hypaque gradient. PBMCs will be cultured for 2 hours at 37°C and 5% CO₂ in a suitable serum-free clinical research medium, AIM-V Clinical Research® (Life Technologies, USA). Non-adherent cells will be discarded, and adherent cells (monocytes) will be cultured in AIM-V supplemented with 500 U/ml of recombinant IL-4 (R&D Systems, INC., MN, USA) and 800 U/ml of GM-CSF (R&D Systems, INC., MN, USA). On the sixth day, monocytes differentiated into dendritic cells will be pulsed with melanoma extracts and then matured with TNF- α (R&D Systems, INC., MN, USA). Flow cytometry will confirm mature dendritic cells' CD14⁻, CD36^{low}, and CD83^{high} phenotype characteristics. Mature DCs will be washed twice and resuspended in 300 μ l of sterile saline. All cell manipulation procedures for vaccine production will be performed under GMP conditions, as indicated.

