- Intercurrent illness that may compromise the patient's life or interfere with the treatment study evaluation
- Requirements for concomitant medication that may interfere with study results.
- Failure to complete the study entirely
- Failure to follow up on the patient.

Sample Size

Recruitment will be conducted to terminate the study after a specific number of patients have been enrolled if a minimum number of responses have not been observed. The lowest significant response rate will be 20% ($\alpha = 0.10$; $\beta = 0.10$). If at least the minimum number of objective responses are observed to complete recruitment, 30 evaluable patients will be enrolled. For example, if there is no response in any of the first 12 treated patients or only 1 out of the first twenty, the study should be terminated. The confidence interval for the response rate is $>20\%$.

Evaluable Patient: An evaluable patient meets the inclusion criteria, does not meet any of the removal criteria, receives all four vaccination cycles, and has been clinically and radiologically followed until the end of this trial.

Study Conduct

- Signing of informed consent
- Complete medical history
- Complete physical examination
- Karnofsky Performance Status measurement
- Estimation of survival quality using the EORTC scale
- If applicable, photographs of the tumor and metastases
- Hematological studies, including albumin and total proteins.
- Electrocardiogram
- CD3, CD4, CD8 cell counts, and total lymphocyte count
- Blood sample collection for in vitro immunological studies.
- Staging radiological studies: Computed tomography of the brain, lungs, abdomen, and pelvis, and bone scintigraphy
- Estimation of metastasis size through physical and radiological examination
- Delayed hypersensitivity test (DTH)

Enrollment

After the procedures mentioned above, each eligible patient will be enrolled. Each patient will be given an identification number. Data will be maintained in a computerized file with restricted access for the research team for each patient.

Patient Monitoring

Patients will be clinically monitored once a week through the following parameters:

- Weight
 - Karnofsky Index
 - Vital signs
 - EORTC Quality of Life Index
 - Comprehensive physical examination
 - Monitoring for toxicity symptoms according to WHO Criteria Grading Toxicities and reporting adverse effects

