- Additionally, they will be evaluated through ELISPOT and ELISA assays, with blood samples taken before each vaccination, to assess the response of specific CTLs to DC stimulation and the presence of cytokines in the patient's serum.

Measurement at the End of Treatment

- Clinical evaluation of the patient
- Estimation of clinical or radiological tumor response: determining tumor volume
- Comprehensive physical examination
- Karnofsky Index
- Photography
- Quality of life and pain assessments
- Delayed hypersensitivity test (DTH): for in vivo response measurement
- Hematological and chemical tests: Assays for measuring in vitro immune response.

Long-Term Follow-Up

Once the patient has completed the full four-cycle treatment, they must be followed up every four weeks for one year. Every two months during the second year. The date of death must be determined in applicable cases. During each visit:

- Directed physical examination
 - Karnofsky Index
 - Estimation of clinical and radiological tumor size
 - Photography
 - EORTC Quality of Life Assessment
 - Reporting of adverse effects
- Clinical Response Assessment

TUMOR RESPONSE CRITERIA

CR: Complete disappearance of the tumor

PR: Tumor regression > 50%

MR: Tumor regression > 25% - <50%

SD: Decrease or growth < 25%

PD: Increase in tumor size during treatment

Statistical Analysis

The primary objective of this study is to estimate the objective response and toxicity associated with treatment using dendritic cells loaded when administered to patients with disseminated melanoma. A stratified recruitment design will be used in this study. In the first stage, 12 patients will be enrolled and treated with loaded dendritic cells. If none of the patients responds to the treatment, enrollment for this study will be terminated. If at least one patient responds to the treatment, the treatment will continue. If, after the enrollment of patient number 20, at least two patients respond to the treatment, the study should continue until a minimum of 30 evaluable patients with 3 out of 4 completed cycles. Assuming that the study will be completed with thirty patients as planned, the 90% confidence interval for the estimated response rate will be 12%, assuming a 20% response rate. If sufficient evidence indicates that the valid response rate is greater than 20%, it would be given if the lower limit of the confidence interval is more significant than 0.20 (alpha = 0.05, 1-tailed -test).

Primary Efficacy Analysis

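### The protocol does not fix one tumour metric for its response cut-offs: volume is named at end of treatment, undefined size elsewhere, and the percentages carry no dimension

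*Protocol*

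**What the plan says.** The protocol describes the tumour measurement differently at different times.

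- **Baseline** (Study Conduct list): "Estimation of metastasis size through physical and radiological examination".
- **End of treatment** (Measurement at the End of Treatment): "Estimation of clinical or radiological tumor response: determining tumor volume".
- **Follow-up visits** (Long-Term Follow-Up): "Estimation of clinical and radiological tumor size".

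The Tumor Response Criteria then give bare percentages: "PR: Tumor regression > 50" per cent, "MR: Tumor regression > 25% - <50" per cent and "SD: Decrease or growth < 25" per cent. Only the progression line names a quantity: "PD: Increase in tumor size during treatment".

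The text seen contains no definition of size, no formula for volume, no rule for combining several lesions and no citation of a response standard. WHO criteria are cited for toxicity only.

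The cut-offs feed the objective response rate: under Clinical Response Measurement, "The percentage of patients with complete response (CR) and patients with partial response (PR) will be reported". The Sample Size and Statistical Analysis sections use the number of responders to stop the trial if there are none in the first 12 patients or only one in the first 20, and otherwise to estimate the rate in 30 evaluable patients and compare it with 20%.

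**The concern.** A percentage regression needs the same quantity before and after. The protocol ties response to volume at one time point but asks for an undefined size at the reference time point and at all later ones. If the site records a diameter at baseline, a volume change cannot be formed reliably afterwards, and no analysis plan can recover a measurement that was never taken.

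The choice matters because a percentage change in diameter, in area and in volume are different things for the same lesion. With looks at 12 and 20 patients that turn on none or one responder, reclassifying one or two patients can decide whether the trial continues. The final rate against 20% would then reflect the metric as well as the treatment.

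**Working it through.** **The plan's own figures.** The protocol gives no figure for the metric itself, so the figures attached to the endpoint are checked first.

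- Stated precision: 90% confidence interval of 12% at a 20% rate with 30 patients. Half-width = 1.645 × √(0.20 × 0.80 / 30) = 0.120. The 12% reproduces.
- Stopping looks: P(stop) = (1−p)^12 + 12p(1−p)^11 × (1−p)^8. At p = 0.20 this is 0.069 + 0.035 = 0.103, in line with the stated β of 0.10.

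The sample-size arithmetic is not affected by this point. What is open is what counts as a response.

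**What the cut-offs mean on each metric.** Input: the 50% and 25% cut-offs from the Tumor Response Criteria. Assumption: the lesion changes evenly in all directions. A fraction c lost corresponds to a diameter fall of 1 − (1−c)^(1/k), with k = 1 for diameter, 2 for the product of two diameters and 3 for volume. Growth of 25% corresponds to a diameter rise of 1.25^(1/k) − 1.

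| Cut-off, as change in diameter | Diameter | Product of two diameters | Volume |
|---|---|---|---|
| 50% regression (PR) | 50.0% fall | 29.3% fall | 20.6% fall |
| 25% regression (MR) | 25.0% fall | 13.4% fall | 9.1% fall |
| 25% growth (SD limit) | 25.0% rise | 11.8% rise | 7.7% rise |

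**One lesion, three categories.** A lesion going from 30 mm to 23 mm has a ratio of 0.767.

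- Diameter: 1 − 0.767 = 23.3% fall, stable disease.
- Area: 1 − 0.767² = 41.2% fall, minor response.
- Volume: 1 − 0.767³ = 54.9% fall, partial response.

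**Illustration only.** The document gives no distribution of tumour change. Assume the change in diameter is normal with SD 30%, and vary the mean. The share called PR is the normal tail beyond −20.6%, −29.3% and −50%. The stopping chance puts that share into the formula above. Each column uses one metric consistently throughout.

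| Assumed mean change | PR share: volume / area / diameter | Chance of stopping early: volume / area / diameter |
|---|---|---|
| +10% | 15.4% / 9.5% / 2.3% | 21.3% / 47.2% / 93.5% |
| 0% | 24.6% / 16.4% / 4.8% | 4.8% / 18.1% / 78.2% |
| −10% | 36.2% / 26.0% / 9.1% | 0.5% / 3.7% / 49.5% |

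Within each row the treatment effect is the same and only the metric differs. The absolute values depend heavily on the assumed mean: the volume share alone runs from 15% to 36%.

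**The case against.** The strongest reply is that the protocol names only one metric, volume, and ties it directly to response. Size is a general word that can include volume, and neither diameter nor area is mentioned as a tumour measure. A reasonable reader could take it that size is estimated at every visit and response is judged on volume. Judging response by volume is a legitimate choice, even though it makes partial response attainable at about a one-fifth fall in diameter. Formulas and lesion-selection rules may also stand in an analysis plan that is not at hand, or in the part of the protocol just before the specific aims, which was not seen.

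Much of this stands, and it rules out two stronger readings.

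- A reader might infer that the 50% threshold is applied to volume at one visit and to a different quantity at the others. The protocol does not say so. No threshold is applied at baseline, which is only the reference, and the PR line names no metric.
- A reader might infer that a site following the plan would score a lesion as PR at end of treatment and as MR or SD four weeks later with no change in it. That requires reading follow-up size as diameter or area, which nothing in the document instructs. Nor does the document say that a later category replaces the end-of-treatment one.

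What the reply does not remove is the gap itself. If size is general, the cut-offs still have no stated metric, and volume is still not called for at baseline. What is measured has to be settled before the baseline scan is read, so this cannot be left entirely to an analysis plan.

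**Conclusion.** The concern holds as an unfixed metric on the primary endpoint, with inconsistent terms across time points. It does not hold as a demonstrated contradiction between two thresholds.

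The firm part is geometric. For evenly shrinking lesions, every diameter fall between 20.6% and 50% is a response by volume and not by diameter, and those between 20.6% and 29.3% are a response by volume and not by area. This reaches the CR plus PR rate, both stopping looks and the comparison with 20%.

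The size of the effect on the trial's response rate cannot be derived from the document. The PR shares and stopping chances above rest on an assumed distribution. They compare three internally consistent metrics and do not measure the effect of switching metric between visits. They show that the choice can matter greatly, not that it has done so here. The point should still be settled before data are collected, because the count is small, the decisions rest on it and the correction is cheap.

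**What to change.** Reconcile the Study Conduct, Measurement at the End of Treatment, Long-Term Follow-Up and Tumor Response Criteria sections by naming one metric. Give its formula and how it is summed over lesions. Require it by the same method at baseline, end of treatment and every follow-up visit, and apply the percentages of every category, progression included, to that sum.

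Two versions would serve:

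1. Keep volume, record it at baseline too, and state that 50% in volume is about a 21% fall in diameter, so that the 20% benchmark is read on that scale.
2. Use the sum, over all measurable lesions, of the products of the two largest perpendicular diameters, and replace the volume and size wording with that term.

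The cost is protocol wording and a case-report-form field; the same examinations and scans serve. The downside is that the response rate may be less favourable if volume is not kept.

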- b) Immediately after treatment, the patient must be monitored. Vital signs should be taken 15 minutes before and after each treatment, and the patient should be observed in the clinic for at least one hour. After the observation period, the patient will be sent home.
- c) Interleukin-2 will be administered subcutaneously, on an outpatient basis, in a properly equipped outpatient clinic for three consecutive days. Vital signs will be monitored, and the patient will be observed in the clinic for 30 minutes.
- d) Patients will be followed to detect and evaluate potential toxic reactions to treatment. The next dose can be repeated the following week if: - There was no grade IV toxicity with the previous treatment, - There was no obvious disease progression - The patient does not meet the exclusion criteria for the protocol.

Inclusion Criteria:

- Patients with histologically confirmed melanoma of the skin: Breslow, Clark, histological type. Location of the primary, clinical, or pathological regional status.
- Complete staging demonstrating the presence of distant metastases, either visceral or in soft tissues or bone tissue: Brain, Lung, Abdomen, and Pelvis CT and bone scintigraphy.
- Objectively measurable disease by clinical or radiological means
- Karnofsky's Performance Status is more significant than 70%
- Life expectancy greater than three months
- Patients over 18 years old
- Informed consent from the patient to participate in the protocol

Exclusion Criteria:

Patients meeting any of the following criteria will be removed from the study:

- Age greater than or equal to 65 years
- Ongoing active infections, including viral immunodeficiency
- Previous chemotherapy within less than two months
- Concomitant malignant tumors (e.g., Chronic Lymphocytic Leukemia, etc.)
- Uncontrolled concomitant diseases (Hypertension, unstable Diabetes mellitus, renal diseases requiring dialysis)
- Situations or conditions requiring urgent surgical intervention, such as intestinal obstruction due to metastasis
- Pregnancy or lactation
- Concurrent participation in other therapeutic research protocols
- Any condition that compromises the objectives of this study.

Removal Criteria from the Study:

Patients will be removed from this study if any of the following conditions occur:

- By the patient's decision to discontinue the study.
- Intolerable adverse reactions, according to WHO Criteria Grading Toxicities

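### Long-term follow-up is ordered only after all four cycles, so overall survival and anything that happens after an early stop may go unrecorded in the patients with the worst outlook

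*Protocol*

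**What the plan says.** The Long-Term Follow-Up section of the protocol begins: "Once the patient has completed the full four-cycle treatment, they must be followed up every four weeks for one year". It continues with "Every two months during the second year" and "The date of death must be determined in applicable cases". It then lists what is done at each visit: physical examination, Karnofsky index, tumor size, photography, EORTC quality of life and adverse effects.

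Other sections determine who reaches that point.

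- Treatment, item d, allows the next dose only without grade IV toxicity after the previous one and if "There was no obvious disease progression".
- Removal Criteria from the Study begins "Patients will be removed from this study if any of the following conditions occur". The list includes "Intolerable adverse reactions, according to WHO Criteria Grading Toxicities" and "Intercurrent illness that may compromise the patient's life or interfere with the treatment study evaluation". It also includes interfering concomitant medication, and not completing the study is itself a criterion.
- Patient Monitoring sets weekly checks during treatment, including EORTC quality of life and WHO-graded toxicity. These are not limited to completers.

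On the endpoints, "Overall Survival" heads the Secondary Specific Aims, which also name disease-free survival and quality of life. Statistical Analysis makes toxicity part of the primary objective.

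**The concern.** The follow-up schedule is tied to finishing treatment, and the reasons for not finishing (progression, severe toxicity, serious intercurrent illness) are prognostic. If the protocol is followed as written, the patients most likely to die early are those for whom no later contact is ordered.

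Two things then happen to overall survival. The patients observed have, by construction, lived through the treatment period. They have also been selected for not deteriorating during it. Both push the reported survival upward. Quality of life after treatment and late adverse effects are selected in the same way.

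The trial is uncontrolled, so no comparison arm would share the bias or reveal it. This is a rule on data collection, separate from the choice of denominator for the response rate. A statistical analysis plan cannot restore death dates that nobody was told to collect.

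**Working it through.** **Plan's own figures.** On this point there are none to reproduce. The protocol gives no planning value for survival and no expected share of early stoppers. Its one precision figure, the 12% half-width for the response rate, reproduces (1.645 × √(0.2 × 0.8 / 30) = 0.120), but the point does not depend on it.

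**Step 1: trace each kind of early stop through the text.**

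| Reason for stopping before cycle 4 | Rule that applies | Follow-up ordered afterwards |
|---|---|---|
| Obvious progression | Treatment, item d: next dose not given. Not a listed removal criterion | None stated; four-cycle condition not met |
| Grade IV toxicity | Treatment, item d; possibly also removal for intolerable reactions | None stated |
| Intolerable reaction, intercurrent illness, interfering medication | Removal Criteria: out of the study | None stated |
| Any other non-completion | Removal Criteria: out of the study | None stated |

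All routes end in the same place. Data up to the stop exist through weekly monitoring; nothing is ordered after it.

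**Step 2: effect of the survival requirement alone.** Assume one exponential hazard for all patients, with follow-up reached by everyone alive at 2 months (Dose and Dosing Rationale puts four cycles in 60 days). With true median M, the share dying before follow-up starts is 1 − exp(−ln2 × 2/M), and the completers' median from first dose is M + 2.

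| Assumed true median | Die before month 2 | Completers' median | 12-month survival, all vs completers |
|---|---|---|---|
| 6 months | 21% | 8 months | 25% vs 31% |
| 9 months | 14% | 11 months | 40% vs 46% |
| 12 months | 11% | 14 months | 50% vs 56% |

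Treatment item d permits dosing the following week. If four doses were given at weekly intervals, the last would fall 3 × 7 = 21 days after the first, and the shift in the median would be about 21/30.44 = 0.7 months instead of 2.

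**Step 3: early stoppers with a worse prognosis.** Assumed inputs: completers survive the first 2 months and then have a median of 9 further months (11 from entry). A fraction f stop early, with median m from entry. For t > 2 months,

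S(t) = (1 − f) × exp(−ln2 × (t − 2)/9) + f × exp(−ln2 × t/m).

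Example with f = 0.2 and m = 3: S(12) = 0.8 × 0.463 + 0.2 × 0.0625 = 0.383. At t = 8.8, the two terms are 0.474 and 0.026, which sum to 0.50, so the median is 8.8 months.

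| Early stoppers (f) | Median, all treated (m = 3 / m = 4) | Completers' median | 12-month survival, all treated | Completers |
|---|---|---|---|---|
| 10% | 9.9 / 10.1 | 11 | 42% / 43% | 46% |
| 20% | 8.8 / 9.2 | 11 | 38% / 40% | 46% |
| 30% | 7.7 / 8.3 | 11 | 34% / 36% | 46% |

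The direction does not depend on these inputs as long as early stoppers survive no better than completers. The size depends on them entirely.

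**The case against.** The strongest case on the other side is that the protocol collects more than the follow-up section alone suggests, and that its wording is loose rather than exclusive. A reader might infer four stronger things that the text does not support.

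- *That quality of life and toxicity are seen only in completers.* They are not. There is a baseline EORTC assessment, weekly monitoring covers both items for everyone under treatment, and Treatment item d calls for follow-up of toxic reactions without conditions. A patient who stops for grade IV toxicity has that event recorded.
- *That deaths of early stoppers are clearly excluded.* The date-of-death sentence is mandatory and does not mention completers; only its position limits it. Deaths during treatment would presumably be known. The fair description is ambiguity.
- *That progression removes a patient from the study.* It is not on the removal list. It withholds the next dose, and so blocks the follow-up condition indirectly.
- *That patients who deteriorate later are censored by removal.* The protocol does not say that the removal criteria operate during long-term follow-up.

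Further, Statistical Analysis counts patients with three of the four cycles as evaluable, and the evaluable-patient definition requires follow-up to the end of the trial. Together these imply that some three-cycle patients are followed, although the same definition also asks for all four cycles. The entry requirement of more than three months' life expectancy should limit deaths during treatment.

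Survival is a secondary aim with no comparator, planning value or decision attached, and no formal tests are planned. With 30 patients, a 95% interval around 46% is about ±18 points (1.96 × √(0.46 × 0.54 / 30) = 0.178), wider than the 3 to 12 points of bias illustrated.

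All of this narrows the point and lowers its weight. It does not supply a rule for following patients who stop early. Sampling error does not excuse a bias that runs in one known direction.

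**Conclusion.** The point holds for overall survival and for observations after an early stop. No section available for review orders vital-status or safety follow-up for a patient who does not finish four cycles, and the removal list takes several such patients out of the study. Part of the protocol just before the visible aims was not available and could not be checked.

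Reported survival would be biased upward by an unknown amount. On the assumed inputs above, the true median is about 1 to 3 months below the 11 months seen in completers, and 12-month survival is 3 to 12 points lower. These figures are illustrations, because the documents give neither a dropout rate nor a survival expectation.

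The change should be made, since the missing data cannot be recovered later. It does not threaten the response-rate objective or the stopping rule.

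**What to change.** Reword Long-Term Follow-Up and Removal Criteria from the Study so that:

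- every patient who receives at least one vaccination is followed for vital status and for unresolved or late adverse effects on the existing two-year calendar, counted from first vaccination, by telephone or record check where a visit is not possible;
- meeting a removal criterion does not end this follow-up unless the patient withdraws consent to it;
- the date-of-death sentence names all treated patients;
- overall survival is reported from first vaccination in all treated patients.

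Also reconcile the four-cycle condition for follow-up, and the four-cycle definition of an evaluable patient, with the three-of-four-cycles wording in Statistical Analysis.

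The cost is wording and some extra contacts. If 30 completers are needed and 10% to 30% stop early (assumed), 30/0.9 to 30/0.7 gives 34 to 43 treated patients, so 4 to 13 early stoppers to trace. Reported survival will look less favourable than in completers alone. No dose or treatment rule needs to change for this.

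### A single reading past the size cut-off counts as an objective response; no repeat is required and no deciding assessment is named, although tumor size is re-measured every four weeks in year one

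*Protocol*

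**What the plan says.** Under Tumor Response Criteria the protocol gives "CR: Complete disappearance of the tumor" and "PR: Tumor regression > 50" percent. No minimum duration, second reading or deciding visit is attached to either.

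These categories form the efficacy endpoint. Under the clinical response aim, "The percentage of patients with complete response (CR) and patients with partial response (PR) will be reported". Statistical Analysis opens with "The primary objective of this study is to estimate the objective response and toxicity associated with treatment". The same responses drive the interim looks: after 12 patients, "If none of the patients responds to the treatment, enrollment for this study will be terminated", and at 20 patients at least two responses are needed to go on to 30.

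Tumor size is measured repeatedly. Measurement at the End of Treatment lists "Estimation of clinical or radiological tumor response: determining tumor volume". Long-Term Follow-Up says that patients who complete four cycles are seen again: "they must be followed up every four weeks for one year", then every two months in the second year. The list for each visit includes "Estimation of clinical and radiological tumor size".

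**The concern.** Tumor size is measured with error, and the response categories turn a continuous quantity into yes or no at one cut-off. A patient whose true regression lies below 50% can be read above it once and so meet the definition. There is no control arm in which such misreadings would also occur, so they enter the primary rate directly. The group most exposed is one that the protocol itself names: minor response, a regression between 25% and 50%.

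At stake is whether the final rate from about 30 patients describes regressions that can be seen twice, or partly reading error. A repeat measurement is already scheduled, but the response definition makes no use of it.

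**Working it through.** **The plan's own figures.** The 90% half-width at a 20% rate with 30 patients is 1.645 × √(0.2 × 0.8 / 30) = 0.120, which matches the stated 12%. At a true 20% rate, the probability of stopping at either look (0 of 12, or at most 1 of 20) is 0.103, against the stated β of 0.10. No stated figure is wrong on this point.

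**Inputs from the protocol.** The cut-off is 50%; the end-of-treatment measurement is on the volume scale; repeats come every four weeks in year one.

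**Assumptions not in the documents.** One measured lesion; log-normal error with standard deviation s = 0.10 to 0.15 per diameter; the baseline is measured with the same error and is shared by all later readings.

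**Formula.** Let r be the true regression and S the error of one size reading on the log scale. For volume, S = s√3 if the three diameters err independently and S = 3s if they err together. Then

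P(one reading shows more than 50%) = Φ(c), with c = [ln 0.5 − ln(1 − r)] / (S√2).

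Two later readings share the baseline error, so their correlation is 0.5 and P(both) is the bivariate normal probability at (c, c).

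Example: for r = 0, s = 0.10 and independent errors, S = 0.173, c = −0.693 / 0.245 = −2.83 and Φ(c) = 0.2%. For s = 0.15 and fully correlated errors, S = 0.45, c = −1.09 and Φ(c) = 13.8%.

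**Volume scale, probability of being called a partial response** (each range runs from s = 0.10 to s = 0.15):

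| True regression | Errors | One reading | Two consecutive | Any of four |
|---|---|---|---|---|
| 0% | independent | 0.2%–3.0% | 0.02%–0.6% | 0.8%–9.1% |
| 0% | correlated | 5.1%–13.8% | 1.3%–5.1% | 14.7%–33.4% |
| 40% | independent | 23%–31% | 11%–16% | 49%–60% |
| 40% | correlated | 33%–39% | 18%–23% | 63%–69% |
| 60% (true PR) | independent | 82%–73% | 71%–59% | 97%–94% |
| 60% (true PR) | correlated | 70%–64% | 56%–48% | 93%–90% |

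**Sensitivity for a stable lesion.**
- Single diameter: at most 0.05% on one reading, which is negligible.
- Area: 0.03% to 1.0% (independent) or 0.7% to 5.1% (correlated).
- Sum of three equal lesions on the volume scale, correlated errors within each lesion: 0.3% to 3.3%. With five lesions: 0.02% to about 1%.

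**Effect on the rate.** Suppose, for illustration, that 3 of 30 patients have a true 40% regression. One volume reading adds 3 × 0.23 = 0.7 to 3 × 0.39 = 1.2 false responders, or 2.3 to 3.9 percentage points. Two consecutive readings add 3 × 0.11 = 0.3 to 3 × 0.23 = 0.7, or 1.1 to 2.3 points.

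**The case against.** **The size is assumed, and may be small.** This stands. The documents give no measurement error. With independent errors or several lesions, a stable tumor is seldom misread. The misreadings that remain are mainly in patients with partial shrinkage.

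**Noise works both ways.** A reader might infer that error only adds responders. It does not: at a true 60% regression one volume reading detects about 64% to 82%, and two fixed consecutive readings 48% to 71%. If one fixed reading decides, the net direction depends on how many patients lie on each side of the cut-off. The upward direction is clear only if a reading at any visit may count.

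**The any-visit reading is not in the text.** A reader might infer that one favourable reading at any of about 20 assessments (1 at end of treatment, 52/4 = 13 in year one, 12/2 = 6 in year two) makes a responder. The protocol neither says so nor rules it out. It mentions tumor response at end of treatment and only tumor size in the follow-up list. The any-of-four column is therefore conditional on that reading. An unseen analysis plan may name the assessment, but the protocol sets the criteria itself, and as written one reading satisfies them.

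**The interim looks.** A reader might infer that noise alone would often carry an inert treatment through. At a 5.1% false-response rate, 1 − (1 − 0.051)^12 = 47% pass the 12-patient look, but only about 24% pass both looks, and at 0.7% fewer than 1% do. A fix that keeps first-observed responses at the looks leaves these figures unchanged, so they do not support it.

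**Responses after other treatment.** A reader might infer that readings after any later anticancer therapy count. The removal criteria already cover concomitant medication that may interfere with results, and an evaluable patient may meet no removal criterion. Surgery or radiotherapy to the measured lesion is not named there, and the response definition itself excludes nothing.

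**Conclusion.** The point holds in limited form. The protocol lets one reading make a responder, names no deciding assessment and requires no repeat, for the efficacy endpoint of an uncontrolled trial. Under the stated error assumptions, confirmation roughly halves false partial responses in patients with a true 40% regression (from about 23%–39% to 11%–23%), and cuts them proportionally more in stable disease, where they are already rare unless the diameter errors are correlated. These figures assume one lesion measured by volume with 10% to 15% error per diameter.

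The documents do not show that the final rate will be inflated by a given amount, or that the interim looks fail because of noise. They show a response rule open to single misreadings, with a repeat measurement available in the schedule that could limit them. It is worth changing, because the change concerns how the primary rate is counted and costs little.

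**What to change.** Add to the response criteria, for the final response rate:

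- Count a complete or partial response only if it is seen again, by the same method, at the next scheduled tumor measurement, at least four weeks later.
- Both readings must precede any other anticancer treatment and any local treatment of the measured lesion.
- Patients without a second measurement count as unconfirmed and stay in the denominator.
- Report the unconfirmed rate beside the confirmed one.

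The 12- and 20-patient looks may use first-observed responses so that recruitment does not wait. The change then protects the final estimate and not the looks.

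**Cost.** A few sentences, and generally no new visit. Two limits should be stated. Four-weekly repeats are scheduled only in year one and for patients who complete four cycles, while Statistical Analysis also counts patients with three of four cycles, so the repeat for those patients needs to be specified. In year two the next measurement comes after two months. Some true responses near the cut-off will not be confirmed, so the confirmed rate will be lower; reporting both rates shows by how much.
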